10.3.2 Protocol Deviations

Any study protocol deviation/violation must be documented in the subject binder, submitted to site's IRB (as per their rules and regulations) and the CCC team for review (see Appendix V). Some of the protocol deviations will also provide a metric for identifying sites that may need further training.

10.3.3 Monitoring

All study sites must permit study-related monitoring by providing direct access to source data and to the subjects' medical histories. The Central Coordinating Center Monitors (Dr. [name], Dr. [name] and [name]) will visit the sites at regular intervals during the study and after the study has completed, as appropriate. During these visits, study worksheets, eCRFs/database entry and supporting documentation related to the study will be reviewed and any discrepancies or omissions will be resolved.

Monitoring visits must be conducted according to the applicable ICH and GCP guidelines to ensure protocol adherence, quality of data, study treatment accountability, compliance with regulatory requirements, and continued adequacy of the investigational site and its facilities.

In addition, because it is required that all of the subject's case report form data not just be entered but also uploaded to the study database in a timely fashion along with any pertinent source documentation, the uploaded documents (i.e. worksheets, admission notes, etc.) will be reviewed by the CCC Multisite Coordinator, [name], against the data entered in the study database to assure for completeness and accuracy of the data in real time. Any queries or concerns will be forwarded to the CCC Principal Investigator, Dr. [name], and as formal queries to each site's coordinator with copy to the corresponding site's Principal Investigator.

Once the subject participant is admitted for the CEA procedure, a de-identified copy of the hospital admission and discharge notes will also be uploaded to the study database and the CCC Multisite Coordinator will review these for adverse events.

Any queries which arise from receipt of the worksheets, eCRFs or hospital notes will allow for continuous data and safety monitoring in real time and not just in preparation for DSMB meetings.

The prevalent errors/omissions/queries found through these monitoring reviews will also be addressed generically during our monthly multi-site team calls as part of our continuing study personnel training.

The payment for subject enrollment and participation will be linked to the timely entering of subject data after each study visit and submission of corresponding source documentation to the study database. This will promote our timely ability to continuously monitor each site for safety, completeness and accuracy of the study data.

11 PARTICIPANT RIGHTS AND CONFIDENTIALITY

11.1 Institutional Review Board (IRB) Review

This protocol and the informed consent documents (Appendix II) and any subsequent modifications will be reviewed and approved by the IRB at Columbia University Medical Center who is responsible for oversight of the study at CUMC. They will also review the individual IRB approval for the other sites that are part of this multisite study.

11.2 Informed Consent Forms

The potential subject participant will be identified by the surgical/clinical team via the planned consultation to discuss undergoing a carotid endarterectomy within. The potential subject participant will be informed about the study, once the potential subject expresses interest in knowing more about the study, the study coordinator and/or doctor will approach the individual and give them the opportunity to participate in this clinical trial. A copy of the consent form will be provided to them, in English or Spanish (whichever is their preferred language), and then the study personnel will facilitate the understanding of the study purpose, procedures and timeline of participation to allow them to make an informed decision about whether or not to participate in this clinical investigation. The information provided will include:

- the purpose and rational of the study
- the clarification that this is an experimental process and not part of the current standard of care
- what their participation process and procedures will be during the study
- the duration of the study participation
- the expected risks and benefits
- the number of study participants expected and approved at the site and at other sites participating in this study
- understanding that they will not incur any additional costs to participate in this study
- clarification of whom they should contact if they experience any adverse reactions and also if they feel they have been harmed in any way due to their study participation
- discuss how confidentiality will be addressed and protected

- details of when a subject's participation may be screened out or considered an OUTCOME by the study investigator without regard to the subject's consent
 - If the MoCA (≤ 25 points) and the AD8 (≥ 2 points) - screen failure
 - If baseline laboratory results indicate existing hepatic or muscle abnormalities that would preclude potentially increasing or adding statins to their current medical regimen (CK $> 5 \times$ ULN and LFTs $> 2 \times$ ULN) – screen failure
 - If the subjects experience stroke or TIA peri-operatively, they will be considered as having reached an OUTCOME in the study.
- explanation that participation is voluntary and that refusal to participate will not create any loss of benefits to which they would have otherwise received:
 - Including the clarification that they can discontinue their participation at any time without affecting their clinical treatment or any other right or benefits to which he/she is otherwise entitled.
 - Details of procedures expected for an orderly termination of the study participation by the individual

Once the study has been explained, the potential subject participants will be asked if they have any questions and given adequate amount of time to ask questions and/or discuss the study with family and friends to decide whether they should participate.

This process will allow sufficient opportunity for the potential participants to provide voluntary, informed consent to participate (or not) and know that they can withdraw at any time without any undue influence or coercion. All participants who consent will be given a copy of the informed consent form for their records and the original consent form will be filed in their study subject binder.

Subjects must provide individual informed consent before any screening tests are performed. When a subject signs the Informed Consent Form (ICF), the subject is considered consented, but not enrolled until they pass the complete screening process for MCI and hepatic/muscle abnormalities (see 6.2.1). Then and only then will they be assigned to a study arm.

In a separate consent form, the participants will be given the opportunity to allow the surplus blood samples obtained from the study to be used in Future Research. This is not required to participate in the main study. If they agree, their surplus samples will be stored at CUMC for future research use. If they do not consent to Future Research, any remaining samples will be destroyed after the study analysis have been completed.

11.3 Participant Confidentiality

All patient information will be coded. Coding involves the replacement of direct patient identifier from data sets with a linking code by which the data remain identifiable. For linking purposes, we use study specific codes, rather than medical record numbers, social security numbers, or other easily decoded combinations of initials and birth dates. The STANCE Subject Code List (Appendix VIII) will be recorded and maintain the subject code-name linking log for their site. Access to the linking files will be restricted to authorized personnel, which will include:

- The National Institute of Health/National Institute of Aging (NIH/NIA, the funding sponsor of this study)
- Institutional Review Board (IRB)
- Members of the study research team at Columbia University Medical Center and members of the study research team at the local sites for participants of the corresponding sites (for safety monitoring purposes)
- Columbia University medical staff, and New York Presbyterian Hospital staff providing treatment for CUMC participants and the local sites' medical staff for participants from the corresponding sites, if necessary
- The Office of Human Research Protections ('OHRP')
- The U.S. Food and Drug Administration (FDA)
- Other regulatory agencies

The data will be collected and stored on an encrypted, password-protected multi-user system. The Statistical Analysis Center (SAC) at the Mailman School of Public Health at Columbia University will create the data management infrastructure for the trial, and will be responsible for creating the electronic database to enter study data and for reporting results to the Data & Safety Monitoring Board (DSMB). All subject research data will be coded with subject ID number. All laboratory and clinical information obtained from this research will be maintained in locked offices and will be accessible only to the main investigators of this project. The electronic database used during the trial is secure and password protected. This webbased system, developed at the SAC, ensures confidentiality and data integrity through the use of a secure server; password protected access, and encrypted data. Specifically, the browser-based front end of the system uses 128 bit Secure Sockets Layer (SSL) technology to ensure that users are properly authenticated to the server and all data exchange occurs in an encrypted fashion. High level of security will be actively maintained. Subjects' information will not be discussed in any form in the presence of other subjects or non-study personnel. Subjects will only be referred to by their subject unique ID number in all study documents. Specimens will be coded using the subject ID number only. For every research participant, relevant clinical information is documented on electronic case report forms and source documents and stored in the secure electronic database or in a double locked area. All study records will be maintained for 7 years. The unique study ID will be generated by the data management system (via the web interface) when a patient enrolls in the study. PHI will be strictly limited to those items essential to the operation of the trial and the specified analyses (dates of diagnosis, dates of treatment, etc.) Clinicians and other personnel involved with patient recruitment, treatment and follow-up will obviously have access to both patient identifiers and the trial data, including the subject ID. Typically, a subject binder/folder is created for each participant, which contains source documents and other information collected for the trial, including subject ID. It is the responsibility of the clinical team to store these folders in a secure place and ensure that they are available only to authorized personnel. Trial personnel not involved in patient contact, including data staff and statisticians, will not have access to identifying information. All trial data, including the subject ID, will be stored on the SAC's secure database servers. The SAC's data systems have been approved for the collection of clinical research data by CUMC IT Security.

11.3.1 Protection while data being collected

Before the data is coded, the subject binders will be kept in a locked cabinet within a locked office to which only the coordinator and approved study personnel have the keys. In addition, any subject contact

information/PHI, if kept digitally, will be kept on an encrypted and password protected computer managed by the study coordinator.

11.4 Study Discontinuation

The study may be discontinued at any time by the IRB, the NIA, the OHRP, the FDA, or other government agencies as part of their duties to ensure that research participants are protected.

Unless altered by the DSMB, the end of study will be when the last subject completes his/her last study visit (approximately one year from their CEA) or final collection of data.

12 ETHICAL CONSIDERATIONS

Investigators must comply with all instructions, regulations, and agreements in this protocol and applicable International Conference on Harmonisation (ICH) and Good Clinical Practice (GCP) guidelines and conduct the study according to local regulations. The Investigator may delegate responsibilities for study-related tasks where appropriate to individuals sufficiently qualified by education, training, and experience, in accordance with applicable ICH and GCP guidelines. The Investigator should maintain a list of the appropriately qualified persons to whom significant study-related duties have been delegated.

12.1 DECLARATION OF HELSINKI

This study will be performed in alignment with the ethical principles outlined in the Declaration of Helsinki.

12.2 ETHICS/IRB COMMITTEE

All site Investigators must obtain IRB approval of the protocol, ICF, and other required study documents prior to starting the study.

If the Site Investigators make any changes to the ICF, the Sponsor must approve the changes before the ICF is submitted to their IRB. A copy of the approved ICF must be provided to the Sponsor. After approval, the ICF must not be altered without the agreement of the relevant IRB and the Sponsor. It is the responsibility of the Investigators to ensure that all aspects of institutional review are conducted in accordance with current applicable regulations.

The Sponsor must receive a letter documenting IRB approval for each site, which specifically identifies the protocol and ICF, prior to the initiation of the study activities. Protocol amendments will be subject to the same requirements as the original protocol.

A progress report must be submitted to the IRB at required intervals and not less than annually.

At the completion or termination of the study, the investigational site must submit a close-out letter to the IRB and provide proof to Sponsor.

12.3 SUBJECT INFORMATION AND CONSENT

Prior to performing any study-related activities under this protocol, including screening tests and assessments, written informed consent with the approved ICF must be obtained from the subject in accordance with local practice and regulations, and authorization to enroll is provided according to the site's local IRB/EC guidelines and requirements for acute clinical trials or by another process compliant with applicable national laws and regulations and IRB/EC requirements. The background of the proposed study, the procedures, the benefits and risks of the study, and that study participation is voluntary for the subject must be explained to the subject or the subject's representative and according to local IRB/EC guidelines or by another process compliant with applicable national laws and regulations and IRB/EC requirements.

A copy of the ICF, signed and dated by the subject according to local IRB/EC must be given to the subject. Each consent form should contain an authorization allowing the Principal Investigator(s) and Sponsor to use and disclose PHI (i.e., subject-identifiable health information) in compliance with local law. The signed consent form will be retained with the study records.

12.4 SUBJECT DATA PROTECTION

Prior to any testing under this protocol, including screening tests and assessments, candidates must also provide all authorizations required by local law (e.g., Protected Health Information authorization - HIPAA). The subject will not be identified by name in the study database or in any study reports, and these reports will be used for research purposes only. The Sponsor, its partners and designees, IRBs, and various government health agencies may inspect the records of this study. Every effort will be made to keep the subject's personal medical data confidential. In addition to using SAC which has been certified as a secure website, we will keep subject contact information and any other subject PHI in a locked cabinet within a locked office and in an encrypted and password protected CUMC desktop.

12.5 COMPENSATION FOR INJURY

In the event of an injury resulting from a subject's participation in this study, you should seek appropriate medical care and inform the study doctor. In the event of an emergency you should go to an emergency room.

If you are injured or harmed as a result of participating in the study and receive medical care through the New York-Presbyterian Hospital (NYPH), a Columbia doctor, or any other health provider, you will be sent a bill for whatever medical care you receive. All or part of your bill may be paid by your health insurance.

Columbia University and New York-Presbyterian Hospital (NYPH) are not offering to provide you the drug/device after the termination of the study or to pay you for pain, worry, lost income, the cost of your medical care or non-medical care costs that might occur as a result of your taking part in this study. However, you do not waive any of your legal rights in signing this form.

12.6 CONFLICT OF INTEREST

The Investigators should address any potential conflicts of interest (e.g., financial interest in

Study drug manufacturer, distributor) with the subject before the subject makes a decision to participate in the study.

12.7. REGISTRATION OF STUDY AND DISCLOSURE OF STUDY RESULTS

The Sponsor has registered the study and will register the post study results regardless of outcome on www.clinicaltrials.gov, a publicly accessible website, in accordance with the applicable laws and regulations.

14 PUBLICATION OF RESEARCH FINDINGS

Publication of the results of this trial will be governed by the policies and procedures developed by the Steering Committee. Any presentation, abstract, or manuscript will be made available for review by the sponsor and the NIA prior to submission.

Appendix I: Schedule of Assessments

Procedure	STUDY DRUG TREATMENT PHASE				D2- D18 CEA DAY	POST CEA FOLLOW UP PHASE					
	Baseline Dose 1	Day 3** +/- 1d	Day 7** +/- 1d	Day 10** +/- 1d		Day 1* (12-25 hours)	Day 7 (+/-3d)	Day 14 (+/-3d)	Day 21 (+/-3d)	Day 30 (+/-5d or PO Visit)	Day 365 (+/-30d)
Informed Consent	X										
Randomization	X										
Study Drug given to subject along with # of capsules to take per dose in the Study Medication Compliance form	X										
Concomitant Medications	X	Any other time the subject states he/she has had a change in medication									
Vitals (height/weight/BP from chart)	X				X	X				X	
Demographics	X										
Education	X										
Medical History (chart/interview)	X	Any other time the subject states he/she has had a change in medical status									
Tobacco Use	X										
Substance Use	X										
CAM	X				X	X				X	

MoCA/AD8 Screening	X											
AMNART or WAT	X											
Neuropsychological Tests (NPT)	X				X	X				X		
TICS-M		X										X
BLESSED ADL		X										X
Safety Questionnaire (CALL)		X	X	X			X	X	X			X
Safety Questionnaire (IN-PERSON)					X	X				X		
Pill Count					X							
CEA Details					X							
Neurological Exam post CEA (chart)					SOC	SOC						
EKG (from chart)	SOC				SOC							
Shipped Lab: ApoE (1x only)	At enrollment or during hospitalization(shipped as ambient blood Monday-Thursday)											
Site Lab: Comprehensive Metabolic Panel	X				X					X		
Site Lab: CK	X				X					X		
Site Lab: Lipid Profile	X				X					X		
Site Lab: CBC with differential	X				X					X		
Site Lab: ESR (Sedimentation Rate)	X				X					X		
Site Lab: C-Reactive Protein	X				X					X		
Site Lab: Urine Pregnancy or Beta-HCG ^A	SOC as part of pre-op labs ^A											
Assess for Adverse Events (AEs)		X	X	X	X	X	X	X	X	X	X	X
Study Completion/Discontinuation	At the end of the subject's participation											

*After surgery ends ** follow-up calls before CEA will be conducted only if not preceded by CEA ^A Urine Pregnancy test or Beta-HCG will be measured only in women of child-bearing age. SOC: Standard of Care

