1.2 Secondary Objectives

- 1) To determine whether a pre-operative statin regimen alters the prevalence of early mortality at Day 365 +/- 30.
- 2) To determine whether differences in eCD/dCD identified in Primary Objectives 1- 4 are associated with either:
 - a. levels of, or peri-operative changes in, ESR/CRP, and/or
 - b. changes in either activities of daily living (BLESSED) or cognition (TICS-M) in the year following randomization and surgery.

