6.3 Local and Central Laboratory Procedures

The participants' three blood draws for Comprehensive Metabolic Panel (CMP), Creatine Kinase (CK), Lipid Profile, CBC with differential, Sedimentation Rate (ESR), C-Reactive Protein (CRP), and their corresponding laboratory tests will be analyzed at each site's institutional laboratory and the results will be recorded in the participant's medical record (source document).

The ApoE blood draw is different as it will only be taken once during the subject's study participation and will be analyzed centrally. Unlike other baseline assessments, this blood draw can be obtained at baseline or at any other timepoint during the subject's participation in the study.

The ApoE blood draw will be shipped to the Central Coordinating Center (CCC) at:

IGM Biobanking Core, CUMC
[name] New
York, NY 10032
Attn: [name].
[contact]

IGM Biobanking will be in charge of receiving ApoE blood samples, extracting the DNA and storing the biological specimens until they are ready to be tested for ApoE. IGM will use the Isolation of (high molecular weight) HMW genomic DNA from blood by using the salting out purification protocol which is a standard DNA isolation method.

The extracted DNA samples will be plated by IGM and sent to LGC Genomics for ApoE allele testing at:

LGC Genomics
Att: [name]
[name]
[name]
[name]
[contact] www.lgcgroup.com

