In general, for the continuous variables, a two-sample Student's t-test will be used for comparing means between the two groups, patients with eCD or dCD and those without eCD or dCD. Non-normally distributed variables will be transformed to improve distributional characteristics. In particular, neuropsychometric test scores will be subjected to a square root transform that yields values that are approximately normally distributed and provide analytic results using parametric tests that are similar to those obtained by non-parametric analysis of the untransformed values. Non-parametric techniques will be used for any variables for which suitable transformations cannot be found. Dichotomous variables will be analyzed using a χ^2 test. Multiple linear and logistic regression models will be used to adjust for the risk factors that are out of balance ($p < 0.10$) between groups. Logistic regression analysis will be used to determine whether any demographic or risk factors other than statin regime significantly affects outcome. Since post-operative pain >4 adversely affects performance, change scores for each test will be obtained using the patients in the reference group, with average pain scores less than 4 as the cutoff value (18).

Missing Data

When data are missing completely at random (MCAR), i.e. when the probability that an outcome is missing does not depend on any outcomes, statistical inference based on completely observed data is valid. If data are missing at random (MAR), i.e. when the probability that an outcome is missing depends on the observed outcomes (such as observed outcome at baseline), inference based on complete data is not valid. We will first check whether the data are MCAR by fitting logistic models for missing data indicators. For example, at the end of the study, the dependent logistic variable is the indicator of whether neuropsychometric test is missing, and the explanatory variables are the outcome at baseline. An insignificant test of the global null hypothesis will confirm MCAR. Assuming the data are not MCAR, we will attempt to obtain bias-corrected estimates under MAR, and we will conduct sensitivity analyses under "non-ignorable missingness".

Interpretation of Results

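### ESR and CRP come from each site's own laboratory, but no analysis described for Secondary Objective 2a contains a site term, so laboratory differences can confound comparisons of levels

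*Combined protocol and SAP*

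**What the plan says.** - **Measurement.** Section 6.3 states that the three routine blood draws, ESR and CRP included, "will be analyzed at each site's institutional laboratory"; only ApoE is central. Appendix I labels the row "Site Lab: C-Reactive Protein". No assay, unit, reporting limit or cross-laboratory calibration is given. Ten sites are listed.
- **Objective.** Section 1.2, item 2a, asks whether eCD/dCD differences are associated with "levels of, or peri-operative changes in, ESR/CRP".
- **Analysis.** No model is written for 2a. The general rule in Section 9.1, largely repeated in 9.5, is: "In general, for the continuous variables, a two-sample Student's t-test will be used for comparing means between the two groups", the groups being patients with and without eCD or dCD. It adds: "Non-normally distributed variables will be transformed to improve distributional characteristics", with non-parametric methods where no transformation works. Regression then adjusts for risk factors that differ between groups at p<0.10. The listed factors are patient characteristics, and centre is not among them.
- **Other descriptions.** Section 2.1.4 says the markers will be correlated with neuropsychometric performance. Sections 9.2 and 9.5 name logistic regression on eCD as the primary analysis for all aims. Neither mentions site.
- **Design.** Section 9.2.1 stratifies randomisation by centre, but no analysis text carries centre into a model.

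**The concern.** Laboratories can differ systematically in what they report for the same blood. If sites also differ in eCD rate, a comparison that ignores site mixes two things: whether patients with eCD have higher CRP than others at the same site, and whether high-reading laboratories happen to serve sites with more eCD. Only the first bears on Objective 2a. Even when eCD rates are equal, laboratory differences widen the spread of the pooled values and make a real association harder to see.

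Unequal eCD rates are plausible on the protocol's own account. Section 2.1.5 expects fewer statin users and lower doses at sites serving underserved populations, and names Buffalo, which is a current site. It reports eCD of 11.0% against 20.2% in asymptomatic patients with and without statins. It gives no between-site figure.

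At stake is the reading of the inflammation result, which Section 2.1.5 regards as important mechanistic data whatever it shows. An artefact could be reported as mechanism, or a real signal missed.

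**Working it through.** The plan gives no power, effect size or error rate for 2a, so there is no figure to reproduce. The check is how far an unadjusted comparison departs from 5% when no association exists.

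**Inputs.** N = 1000 and ten sites are from the protocol; equal sites of 100 are assumed. The eCD rate p = 0.12 is from Section 2.1.5 (2007–2012). The laboratory SD σ_L, in units of the within-site SD, and the between-site SD of the eCD rate, σ_p, are assumptions.

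**Closed form.** With S equal sites, the spurious part of the pooled difference in means is

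B = Σ o_s(p_s − p) / [S·p(1 − p)],

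where o_s is the laboratory offset and p_s the eCD rate at site s. If the two are independent,

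SD(B) ≈ σ_L·σ_p·√(S − 1) / [S·p(1 − p)].

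The standard error used by the test is √[(1 + 0.9σ_L²)(1/120 + 1/880)], the factor 0.9 being (S − 1)/S.

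For σ_L = 0.5 and σ_p = 0.06:
- SD(B) = 0.5 × 0.06 × 3 / (10 × 0.12 × 0.88) = 0.0852
- SE = √(1.225 × 0.00947) = 0.1077
- inflation k = √[1 + (0.0852/0.1077)²] = 1.275
- rejection = P(|Z| > 1.96/1.275) = 12.4%

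**Simulation, levels** (4000 null trials per setting, p = 0.12):

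| σ_L | σ_p (points) | Closed form | Pooled t-test | With site term |
|---|---|---|---|---|
| 0.3 | 3 | 5.7% | 5.2% | 4.5% |
| 0.3 | 6 | 8.0% | 6.7% | 4.4% |
| 0.5 | 3 | 6.8% | 6.5% | 4.9% |
| 0.5 | 6 | 12.4% | 12.5% | 5.1% |

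The Monte Carlo standard error near 5% is √(0.05 × 0.95/4000) = 0.34 points. The closed form and the simulation differ by up to 1.3 points, so the middle rows should not be read more finely than that. A second set of simulations at an 11% eCD rate gave 5.5% (σ_L 0.2, σ_p 3 points) to 13.2% (0.5, 7 points) for the pooled test, and 4.2% to 5.2% with a site term.

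**Equal eCD rates.** With σ_p = 0, B is zero. The pooled test rejected in 4.9% to 5.6% whatever the laboratory offset. Only precision suffers: the variance is multiplied by 1 + 0.9σ_L², which is 1.036 at σ_L = 0.2 and 1.225 at 0.5. The information loss is about 3% and 18% (1 − 1/1.036 and 1 − 1/1.225).

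**Transformation or ranks.** At σ_L = 0.5 and σ_p = 5 points (3000 runs), a pooled t-test on the log scale rejected in 9.0%, a pooled rank test in 8.8% and a site-adjusted model in 5.4%. Neither transformation nor ranking removes a site offset.

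**Change within a patient.** An additive offset cancels: the pooled test gave 4.7% to 5.7%. A multiplicative offset does not cancel in untransformed change (up to 10.9%), but it does in log change. Both statements assume one laboratory per patient, which fits Section 4.3, where even home-drawn samples go to the site's clinical laboratory.

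**The case against.** The strongest reply is that the plan never commits to the faulty analysis. The t-test is a general default, Section 2.1.4 speaks of correlation, and Sections 9.2 and 9.5 speak of logistic regression. Ignoring site is therefore inferred from silence. That is correct as far as it goes. But all three descriptions omit site, so each is open to the same confounding, and the adjustment rule does not list centre. Three descriptions and no named model are themselves a reason to write one.

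A reader might infer that untransformed values will be pooled. The documents do not support this, since Section 9.1 provides for transformation and rank methods. A reader might also take the limits for CK and liver tests in Section 7.2.1, set as multiples of the laboratory's upper limit of normal, as a harmonisation method withheld from ESR and CRP. Those multiples are screening and adverse-event thresholds, not an analysis method.

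The reply is also right that the size rests on assumptions. The top of the range needs both extremes. On a log scale with within-site SD 1, a laboratory SD of 0.5 means that a laboratory one SD high reads about 65% high (e^0.5 = 1.65). An eCD SD of 7 points around 11% puts sites one SD either side of the mean at 4% and 18%. At the low end the inflation cannot be told from 5%.

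Finally, half of the objective concerns change, which is largely protected on the right scale. That stands, but levels are named too and no scale for change is fixed.

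**Conclusion.** The point holds in a limited form. ESR and CRP are measured locally without harmonisation, and no described analysis accounts for site. Confounding of levels then needs two further conditions, laboratory offsets and unequal eCD/dCD rates between sites, and the documents quantify neither. Over the assumed ranges the type I error is about 5% to 13% unadjusted and about 5% with a site term. If eCD rates are equal, the only effect is lost precision.

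A reader might infer that a false inflammation finding is likely, or that the trial's whole mechanistic case depends on 2a. Neither follows. The upper figure is a corner of an assumed range, and Primary Objective 2 also asks a mechanistic question, about blood-brain-barrier penetration. The primary eCD/dCD comparisons do not use these markers and are unaffected. This is a modest weakness in a secondary objective, worth correcting because the remedy is only wording.

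**What to change.** In Section 9, add an analysis for Secondary Objective 2a: a linear model for log ESR and log CRP with eCD (or dCD) status and site as terms, fitted to levels and to log change from baseline. Align Section 2.1.4 with it.

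The cost is wording and about nine degrees of freedom (ten sites less one) out of roughly 1000 patients, with no new samples or visits. The estimate becomes a within-site association, so any genuine between-site relation between inflammation and eCD is set aside.

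Three additions are optional: a left-censoring rule for results below a laboratory's reporting limit (which a site term does not handle), a van Elteren test stratified by site as a rank-based alternative, and eCRF fields for each site's assay type and reporting limit.
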